9.3 Other Events to be Reported

Overdose, medication error, misuse and abuse will not be reported since no IMP is given in this trial.

9.3.1 Pregnancy

Any pregnancy occurring during the main trials (LP0084-1193, -1194, -1195 and -1196) from Visit 1 until Visit 7 has been reported. This extension protocol investigates subjects following their participation in one of the four pivotal phase 3 trials without any additional treatment, hence pregnancies are not to be reported in the current trial as treatment has been finalised 14 months prior to enrollment.

Trial ID: LP0084-1369	Date: 25-Jul-2017	Version: 2.0 Page 21 of 52
-----------------------	-------------------	-------------------------------

9.3.2 Aggravation of Condition

Any clinically significant aggravation/exacerbation/worsening of any medical condition(s), compared to baseline, must be reported as an AE.

9.3.3 Adverse Events of Special Interest

Due to the sun-damage, the target population is prone to SCC development. Sun-damaged skin is also prone to development of keratoacanthoma (KA) as a response to local irritation and/or inflammation. To ensure that all information relevant for surveillance is collected, SCCs and KAs in the area treated in the pivotal phase 3 trials are considered adverse events of special interest (AESI).

For SCCs and KAs in the area treated in the confirmatory phase 3 trials (LP0084-1193, -1194, -1195, -1196), the relevant information will be collected in the CRF. In addition, the local histology report should be faxed or emailed to Global Pharmacovigilance, once available, using the following fax number or email address:

[contact]

Email address: [contact]

SCCs and KAs in the treatment area (defined in the main phase 3 trials) that meet the criteria for being serious should be reported as SAEs (please refer to section 9.4.1 for reporting details).

The pathology slides that have been used for the initial diagnosis of the AESI will be sent for central pathology review by the procedure outlined in section [8.4](#)

9.4 Additional Reporting Requirements for Serious Adverse Events

9.4.1 Investigator Reporting Responsibilities

When reporting SAEs, the paper SAE Form – Clinical Trials, must be used, and submitted to LEO within 24 hours of first knowledge. This report should contain an assessment of available information on seriousness, severity, causal relationship to the IMP, comparator or trial procedure, the action taken, the outcome to date, and a narrative description of the course of the event.

The completed SAE form must be faxed or scanned and e-mailed to Global Pharmacovigilance, LEO using the following fax number or e-mail address:

Trial ID: LP0084-1369	Date: 25-Jul-2017	Version: 2.0 Page 22 of 52
-----------------------	-------------------	-------------------------------

[contact] (for Global Pharmacovigilance)

E-mail address: [contact] (for Global Pharmacovigilance)

It may be relevant for the (sub)investigator to enclose other information with the SAE form, such as anonymised reports of diagnostic procedures, hospital records, autopsy reports, etc.

Additionally, Global Pharmacovigilance, LEO may request further information in order to fully assess the SAE. The (sub)investigator must forward such information to Global Pharmacovigilance, LEO upon request by fax or e-mail (see contact details above).

The investigator must notify the local IRB(s)/IEC(s) of SAEs as required by current applicable legislation for the concerned country.

SAEs occurring after the completion of the clinical trial including any protocol required post-treatment follow-up period should not be routinely sought or collected. However, such events should be reported to Global Pharmacovigilance, LEO ([contact]) if the (sub)investigator becomes aware of them.

9.4.2 LEO Reporting Responsibilities

Global Pharmacovigilance, LEO is responsible for assessing whether or not an SAE is expected. The relevant reference document for this clinical trial is:

For the IMP, the Investigator's Brochure, LEO 43204, Field Therapy, Edition No. 5 and subsequent updates hereof must be used (9).

Global Pharmacovigilance, LEO will notify the regulatory authorities and concerned investigators of SAEs according to the current applicable legislation for the concerned countries.

The IRB(s)/IEC(s) will be notified of SAEs according to the current applicable legislation for the concerned countries.

For all non-US countries, all SAEs which are assessed as casually related to the IMP by either the investigator or LEO (ICH E2A Guideline), and which are unexpected (Suspected, Unexpected Serious Adverse Reactions (SUSARs)), are subject to expedited reporting to regulatory authorities and IRB(s)/IEC(s) according to the current applicable legislation in the concerned countries. Investigators will be notified of these on an ongoing basis.

Trial ID: LP0084-1369	Date: 25-Jul-2017	Version: 2.0 Page 23 of 52
-----------------------	-------------------	-------------------------------

For the US, all SAEs which are assessed as casually related to the IMP by LEO (Guidance for Industry and Investigators – Safety Reporting Requirements for INDs and BA/BE Studies) and which are unexpected (Serious and Unexpected Suspected Adverse Reactions (IND safety report)) are subject to expedited reporting to regulatory authorities and IRB(s)/IEC(s) according to the current applicable legislation in the concerned countries. Investigators will be notified of these on an ongoing basis.

9.5 Follow-up for Final Outcome of Adverse Events

During the trial, the investigator should follow up for final outcome on all AEs (including SAEs). Once a subject leaves the clinical trial, the investigator should follow up on the outcome of all non-serious AEs classified as of possible/probable relationship to the investigational product for 2 months or until the final outcome is determined, whichever comes first. SAEs must be followed up until a final outcome has been established, i.e. the follow-up may continue beyond the end of the clinical trial.

10 Trial Product

Not applicable

11 Statistical Methods

Data on skin neoplasia from the 14 months observation time in the confirmatory phase 3 trials LP0084-1193, -1194, -1195, and -1196 will be combined with the data from the present trial.

11.1 Sample Size

No formal sample size calculation has been made. The sample size is determined by the number of subjects who complete Visit 11 in the pivotal phase 3 trials (LP0084-1193, -1194, -1195, -1196) and are willing to enter the extension protocol. Two thirds have been treated with ingenol disoxate, one third with vehicle.

A total of 1200 subjects were planned be enrolled in the pivotal phase 3 trials (LP0084-1193, -1194, -1195, and -1196) and randomised 2:1 to the two treatment groups ingenol disoxate gel or vehicle gel. With 800 subjects in the ingenol disoxate treatment group and 400 subjects in the vehicle gel group, an adequate precision of the 3-year plus 2 months incidence rate can be obtained. Assuming a 3-year plus 2 months rate of 4.0%, the upper 95% confidence limit will on average be 5.36% for ingenol disoxate gel and 5.92% for vehicle gel, and assuming a 6.0% rate, the upper 95% confidence limit will on average be 7.65% for ingenol disoxate gel and 8.33% for vehicle gel.

Trial ID: LP0084-1369	Date: 25-Jul-2017	Version: 2.0 Page 24 of 52
-----------------------	-------------------	-------------------------------

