6.3 Sample Size

No formal sample size calculation has been made. The sample size is determined by the number of subjects who complete Visit 11 in the confirmatory phase 3 trials (LP0084-1193, -1194, -1195, -1196) and are willing to enter the extension protocol. Two thirds would have been treated with ingenol disoxate, one third with vehicle.

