11.3.3 Exposure and Treatment Compliance

11.3.4 Analysis of Primary Endpoint

The null hypothesis is that there is no difference in time to first SCC between ingenol disoxate gel and vehicle gel. The hypothesis will be tested against the two-sided alternative that there is a difference between the two treatment groups.

Primary endpoint is time to first SCC in the treatment area from Visit 2 in trials LP0084-1193, -1194, -1195 and -1196.

Only the SCC confirmed by the IAC will be used in the primary endpoint analysis.

The annual and the 3-year and 2 months cumulative incidence of first event of SCC will be calculated for each treatment group (active and vehicle) in main trial using methods of survival analysis in the presence of censoring. The cumulative incidence rates will be presented by treatment group for the event of first SCC as primary endpoint. A proportional hazards model will be fitted if the model assumptions are valid. Log-rank test comparing the two treatment groups will be performed. For descriptive purposes, as an additional analysis, the difference in cumulative incidence rates between the two arms will be estimated and presented together with its 95% confidence interval. A landmark analysis will additionally be performed in order to exclude SCC and other neoplasia reported within the first 8 weeks which are not assumed to be associated with the trial treatment. This corresponds to left-truncation of the trial period at 8 weeks, the analysis will otherwise be conducted as above. Patients who experience a SCC before the 8-week landmark time point are excluded from the landmark analysis.

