11.3.9 Handling of Missing Values

Missing values for time to occurrence of SCC or other neoplasia will be handled as censored observations.

12 Trial Committees

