7.2.1 Primary Efficacy Criterion

The primary endpoint will be analysed as described in the clinical trial protocol (CTP).

The proportional hazards model will include planned treatment as explanatory variable, and have the proportional hazards assumptions checked by assessing whether or not the survival functions cross each other. The hazard ratio and corresponding 95% Wald confidence limits will be estimated within the proportional hazards model with planned treatment group as explanatory variable. A likelihood ratio test within the proportional hazards model will be applied for comparison of treatment groups. The results will be presented by treatment location (face/chest or scalp) and treatment group within treatment location as well as overall by treatment group (ingenol disoxate versus vehicle). The analysis will be based on the FAS.

The cumulative incidence rate will be calculated as the number of subjects with one or more events divided by the total observation period across all subjects in the FAS. The lower and upper limits of the 95% confidence interval will be calculated using the following SAS code:

Lower=((cinv(0.025,#subjects*2)/2)/total_obs_period)

Upper = ((cinv(0.975,2*(#subjects+1))/2)/total_obs_period)

The cumulative incidence rate and corresponding 95% confidence interval will also be presented by treatment location (face/chest or scalp) and treatment group within treatment location as well as overall by treatment group (ingenol disoxate versus vehicle).

For the landmark analysis described in the CTP time=0 will be defined as the date of visit 7 (week 8). This analysis will be based on the follow-up analysis set (FUAS) excluding subjects who experience an event prior to visit 7. Subjects in FUAS who do not have a visit 7, will have the date of their visit 7 imputed as the date of their visit 6 (week 4) plus 28 days.

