7.4 General Principles

7.4.1 Handling of Drop-outs and Missing Values

Relatively few subjects in the FAS are expected to experience an event of SCC or other skin neoplasia, and therefore the amount of censoring in the analyses of the primary and secondary endpoints is expected to be substantial. All subjects who completed the 4 main trials without a prior event of SCC or other skin neoplasia and choose not to participate in the extension trial will be censored at the time they complete the main trial. All discontinued subjects without a prior event of SCC or other skin neoplasia will be censored at the time of discontinuation from the trial. The survival analyses performed will be evaluated in the presence of censoring.

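### The upper confidence limits in Protocol 11.1 assume complete 38-month follow-up without saying so, while the plan censors non-entrants and dropouts

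*Protocol*

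**What the plan says.** Protocol 11.1 reports that no formal sample size was calculated. It takes the 1200 subjects planned for the four main trials, randomised 2:1, and states that with 800 and 400 subjects "an adequate precision of the 3-year plus 2 months incidence rate can be obtained". The support is four expected upper limits for the 38-month rate. The first reads "Assuming a 3-year plus 2 months rate of 4.0%, the upper 95% confidence limit will on average be 5.36% for ingenol disoxate gel". The others are 5.92% for vehicle at the same 4% rate, and 7.65% and 8.33% for ingenol disoxate and vehicle at a 6% rate. No formula, entry fraction or dropout fraction is given.

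Other sections describe follow-up that is not complete:

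- Protocol 6.3: "The sample size is determined by the number of subjects who complete Visit 11 in the confirmatory phase 3 trials" and who are willing to enter the extension. Section 11.1 says the same.
- Protocol 11.2: the full analysis set (FAS) is all randomised subjects, so non-entrants stay in the analysis.
- Protocol 11.3.4: cumulative incidence is estimated "using methods of survival analysis in the presence of censoring".
- Protocol 11.3.9: "Missing values for time to occurrence of SCC or other neoplasia will be handled as censored observations".
- SAP 7.4.1: event-free main-trial completers who "choose not to participate in the extension trial will be censored at the time they complete the main trial". For the rest, "All discontinued subjects without a prior event of SCC or other skin neoplasia will be censored at the time of discontinuation from the trial". The section expects a substantial amount of censoring.
- SAP 7.2.1: the incidence rate is "calculated as the number of subjects with one or more events divided by the total observation period across all subjects in the FAS", with chi-square limits written out in SAS code.

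**The concern.** A binomial limit with n = 800 or 400 describes the expected precision only if every randomised subject is followed to the end of the period or to the event. Here follow-up beyond Month 14 is voluntary, and those who do not continue are censored with 24 of the 38 months still to run. The expected limits must then be higher than stated. The error runs in one direction, and it is larger in percentage points in the smaller vehicle arm.

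Because there is no formal sample size calculation, these four figures are the only quantitative support for the trial's size. Protocol 3.3 gives as one reason for the extension the need for a large, well-controlled trial to answer concern about SCC after treatment. A reader who takes the limits at face value will expect tighter intervals than the design can give.

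**Working it through.** **Inputs.** From Protocol 11.1: n = 800 and 400, and 38-month rates p of 4% and 6%. From Protocol 3.3: total follow-up of 38 months (14 in the main trial, 24 in the extension). From Protocol 11.3.8: 95% confidence, hence 1.96. From SAP 6.1 and 6.2: 562 entrants and an FAS of 1234, so 562/1234 = 45.5%.

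**Step 1: reproduce the stated figures.** Upper limit = p + 1.96 × sqrt(p(1−p)/n).

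- 4%, n = 800: 0.04 + 1.96 × sqrt(0.0384/800) = 5.36%
- 4%, n = 400: 0.04 + 1.96 × sqrt(0.0384/400) = 5.92%
- 6%, n = 800: 0.06 + 1.96 × sqrt(0.0564/800) = 7.65%
- 6%, n = 400: 0.06 + 1.96 × sqrt(0.0564/400) = 8.33%

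All four match. Exact binomial, Wilson, exact Poisson, one-sided and continuity-corrected limits do not.

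**Step 2: allow for censoring.** Let S(t) be the event-free probability with constant hazard λ = −ln(1−p)/38 per month, and G(t) the fraction of randomised subjects still uncensored. The Greenwood variance of the Kaplan-Meier estimate at Month 38 is

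Var = S(38)² × ∫₀³⁸ λ / (n G(t) S(t)) dt.

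With G = 1 this returns the Step 1 values exactly. If the only loss is non-entry at Month 14, with fraction e entering, it reduces to

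Var = S(38)² × {[1/S(14) − 1] + [1/S(38) − 1/S(14)]/e} / n.

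Hand check at p = 4%, n = 800, e = 0.455: S(14) = 0.96^(14/38) = 0.9851, so the brackets are 0.01515 and 0.02651. Var = 0.9216 × (0.01515 + 0.02651/0.455)/800, giving SE = 0.92% and an upper limit of 5.80%. The other three limits are 6.55%, 8.19% and 9.09%.

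The table adds assumed main-trial loss: 90-95% retained to Month 14, lost linearly or front-loaded (an assumed 95% left at Week 8). Entry is a share of all randomised subjects, equal in both arms, and all entrants are followed for 24 months. Values are ingenol disoxate / vehicle.

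| Entry | SE at 4% (%) | Upper at 4% | SE at 6% (%) | Upper at 6% | Points above stated |
|---|---|---|---|---|---|
| Complete | 0.693 / 0.980 | 5.36 / 5.92% | 0.840 / 1.187 | 7.65 / 8.33% | 0 |
| 90% | 0.720-0.726 / 1.018-1.027 | 5.4 / 6.0% | 0.873-0.880 / 1.234-1.244 | 7.7 / 8.4% | 0.05-0.11 |
| 70% | 0.784-0.790 / 1.109-1.117 | 5.5 / 6.2% | 0.951-0.958 / 1.345-1.354 | 7.9 / 8.6% | 0.18-0.33 |
| 45.5% | 0.922-0.927 / 1.304-1.311 | 5.8 / 6.6% | 1.118-1.124 / 1.582-1.590 | 8.2 / 9.1% | 0.45-0.79 |

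Standard errors grow by about 4-5%, 13-14% and 33-34% in the last three rows.

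**Step 3: the interval written out in SAP 7.2.1.** Upper = χ²(0.975; 2(d+1)) / (2 × PT), with expected events d = n∫λSG dt and person-time PT = n∫SG dt. With complete follow-up at 4%, d = 32/16 and PT = 2482/1241 person-years. At 6%, d = 48/24 and PT = 2457/1228. Limits per 100 person-years, ingenol disoxate / vehicle:

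| Entry | 4% (true rate 1.29) | 6% (true rate 1.95) |
|---|---|---|
| Complete | 1.82 / 2.09 | 2.59 / 2.91 |
| 90% | 1.85 / 2.14 | 2.62 / 2.96 |
| 70% | 1.90 / 2.22 | 2.68 / 3.05 |
| 45.5% | 1.98 / 2.36 | 2.78 / 3.20 |

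Converted to 38-month risk for comparison only, as 1 − exp(−upper × 38/12) with the upper limit per person-year, complete follow-up gives 5.6/6.4% and 7.9/8.8%. Entry of 45.5% gives 6.1/7.2% and 8.4/9.6%. The interval the SAP specifies is therefore wider than 11.1 implies even before any censoring.

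**The case against.** The best defence is that 11.1 contains no arithmetic error and hides no inputs. It names 800 and 400 as planned main-trial numbers, and the same section says that extension size depends on who is willing to enter. That holds for the arithmetic. It does not cover a precision presented as the expected one under a plan that cannot attain it unless everyone enters and stays.

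Second, nothing depends on the figures: no recruitment target, stopping rule or success criterion uses them, no threshold defines adequate, and the report will show the achieved intervals. All of this is correct and limits the importance of the point. The SAP's remark on censoring is a disclosure, but it does not revise the limits.

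Third, the large gap is hindsight. The 562/1234 comes from the SAP of 27 May 2018, about ten months after protocol version 2.0. It may partly reflect the early stop noted in SAP section 5, and the scenario still credits all entrants with 24 months. This stands: 45.5% shows what low entry does and is not evidence of a planning error. The 70% value is also an assumption.

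Fourth, at 90% entry the censoring effect (0.05-0.11 points) is smaller than the difference between the Wald and exact binomial limits with complete follow-up (5.60/6.42% and 7.88/8.80% exact, so 0.23-0.49 points). This is true, and it is a reason for the restatement to name its estimator.

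**Conclusion.** The four limits are correct for complete follow-up, but they are presented as the precision to be expected from a plan that censors every non-entrant and dropout. They are an unlabelled best case. The understatement is about 0.1 point or less at 90% entry, 0.2-0.3 points at 70%, and 0.45-0.8 points at 45.5%. These sizes rest on constant hazard, non-informative censoring, equal entry by arm, 90-95% retention to Month 14 and full extension follow-up for entrants. The documents give none of these. The direction does not depend on the retention or entry fractions chosen: with non-informative censoring, any loss widens the interval.

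The limits also do not correspond to the person-time interval in SAP 7.2.1, so the documents give no expected precision for that interval. The point should be corrected because these are the plan's only precision figures. It changes no analysis and no decision rule.

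**What to change.** In Protocol 11.1 or the SAP:

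1. Label the present limits as assuming that all randomised subjects are observed to Month 38 or first SCC.
2. Restate them for a range of entry fractions, expressed as a share of randomised subjects (for example 90%, 70% and the reported 562/1234), with the retention assumption stated. Use Kaplan-Meier with Greenwood variance for the cumulative incidence in Protocol 11.3.4, and the chi-square person-time interval for the rate in SAP 7.2.1.
3. Base the statement on adequate precision on the restated figures.

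Step 1 alone is one line and removes the misstatement, but leaves the adequacy claim without support for the follow-up actually planned. The full change costs one paragraph and a short calculation, with no extra patients, visits or analyses. The only drawback is that the stated precision becomes less favourable.

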11.2 Trial Analysis Sets

All subjects enrolled in the trial (i.e. subjects for whom informed consent has been obtained and who have been registered in a clinical trial) will be accounted for in the clinical trial report.

All randomized subjects from the pivotal phase 3 trials (LP0084-1193, -1194, -1195, -1196) are included in the full analysis set (FAS) and will be analysed for incidence of SCC and other skin neoplasia. Exclusions from the full analysis set can be considered in special cases as described in ICH E9, section 5.2.1., Full Analysis Set. If it is decided to exclude a subject from the full analysis set, a justification addressing ICH E9 will be given.

A safety analysis set will be defined by excluding subjects from the full analysis for whom no post-baseline safety evaluations are available.

The decisions regarding inclusion/exclusion of subjects and/or subject data from the trial analysis sets will be documented in the statistical analysis plan update .

11.3 Statistical Analysis

11.3.1 Disposition of Subjects

The reasons for leaving the trial will be presented for the FAS by last visit attended and by treatment group in the main trial. This will also be done for the enrolled and eligible subjects not included in the FAS.

11.3.2 Demographics and other Baseline Characteristics

Descriptive statistics of demographics and other baseline characteristics will be presented for all subjects, by treatment group in the main trial and by country. Presentations of age, sex, ethnicity and race and baseline AK count by treatment group will also be given by main trial.

The demographics and other baseline characteristics will be summarised for the 4 main trials combined as well as the subset of those who enter the extension trial.

Demographics include age, sex, race, ethnicity and skin type. Other baseline characteristics include anatomical location (face, chest, or scalp) of treatment area in the main trials, treatment area size, concurrent diagnoses (from medical history and indications for concomitant medication), and concomitant medication. Baseline AK characteristics will include baseline AK count for the treatment area, duration of disease, previous treatment of

Trial ID: LP0084-1369	Date: 25-Jul-2017	Version: 2.0 Page 25 of 52
-----------------------	-------------------	-------------------------------

AKs (anywhere) and previous treatment of AKs in the treatment area as reported in the main trial.

